A gram stain from the study product and placebo will be performed and resulted prior to infusion of the study product or placebo to indicate sterility. If the gram stain is positive, then the cells or placebo will not be infused and the cord blood is discarded. If sterility cultures, which will be performed on the collected cord blood at Duke University Stem Cell Laboratory (STCL), subsequently become positive, the study team will notify the clinical team of the nature of the positive culture and a follow up strategy will be developed by the clinical and research teams. In general, babies with HIE are placed on empirical antibiotic therapy shortly after birth. If the baby is on concurrent antibiotic therapy and if the antibiotic covers the organism grown in the culture obtained from the cord blood, the baby will complete a course of therapy. If, on the other hand, the baby is no longer on antibiotics or the organism identified in the culture is not sensitive to the antibiotics the baby is being treated with and is not considered a contaminant, a course of antibiotic therapy covering the organism isolated will be administered.

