8.3. SHIPMENT OF REMAINING CORD BLOOD PRODUCTS TO DUKE FOR CRYOPRESERVATION

The entire cord blood unit or cord blood remaining after processing and removal of cells for dosing and the remaining material in the PRBC bags and plasma bags from remote sites will be shipped to the Stem Cell Transplant Laboratory at Duke University for cryopreservation and testing for potential future autologous use by the study subject. Each infant's cord blood unit's characteristics will be recorded, including total nucleated cell counts pre- and post-processing, post-processing viable CD34⁺ cell content, colony forming units, sterility, and viability. The manual of procedures describes packing and shipping to STCL at Duke University. Cryopreservation is dependent on receipt of cord blood or processed cord blood within 96 hours of collection at STCL at Duke University. It is best to ship as soon as possible to preserve the viability and potency of the cord blood cells.

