9. SCHEDULE OF EVENTS

	First Dose<40 hours postnatal if two doses are feasible <48 hours if only one dose is feasible	Second dose if feasible < 48 hours postnatal	Rewarming through postnatal day 21	Visit 1 12-16months
Screening	X			
Maternal consent or assent	X			
Collect UCB	X			
Labs ¹	X			
Blood Gas ²	X			
Neurological Assessment ³	X	X	X	X
Infusion and vitals ⁴	X	X (if cells are available)		
History and Physical Exam	X			X
Adverse events and concomitant meds	X	X	X	X
MRI			X	
PT/PTT ⁵	X		X	

¹ Serum Electrolytes, BUN, CBC, Creatinine, liver function obtained as part of routine care for HIE (section 8.5.2) ² Collected daily (section 8.5.3) ³ Collected at baseline, daily during cooling and prior to discharge (section 8.5.4) ⁴ Assessed pre-infusion and for 15min post infusion and per hospital SOC (section 8.5.1) ⁵ Collected during cooling and 24 hours after re-warming if obtained as part of routine care (section 8.5.5)
				

A Phase II Multi-site Study of Autologous Cord Blood Cells for Hypoxic Ischemic Encephalopathy (HIE) IND 14753 (BABYBAC II)

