13.3. UNBLINDING

Safety or other clinical or legal considerations including requests from a child's family may, on rare occasions, require unblinding of the infant with regard to the actual intervention received. If such events make it necessary, the lab staff, responsible for preparation of study product at each site will be able to unmask the study drug product given to an individual infant. Before unblinding the lab staff must contact the Center's Investigator and the overall study Principal Investigators prior to releasing this information, and a protocol violation form will be completed.

13.4.INTERIM MONITORING FOR SAFETY OUTCOMES

The intervention for this trial will be conducted during the first 48 hours of life for the study subjects, while the primary outcome will be assessed at 12 (12 – 16) months of age. Thus, the primary focus of interim monitoring for this trial will be based on monitoring adverse events within 24 hours of cord blood infusion. Adverse events monitored will include the following, plus a composite (any of the listed events), on which statistical comparisons between the treatment groups will be based:

- Acidosis
- Allergic reaction/hypersensitivity
- GI Pathology
- Hemoglobinuria
- Hyperglycemia

A Phase II Multi-site Study of Autologous Cord Blood Cells for Hypoxic Ischemic Encephalopathy (HIE) IND 14753 (BABYBAC II)

- Hypoglycemia
- Hypertension
- Hypotension, and fever in the absence of neutropenia
- Hypoxia
- Infectious Disease
- Polycythemia
- Pulmonary Hypertension, within the first 24 hours
- Sinus bradycardia
- Sinus tachycardia
- Dyspnea
- Any other cardiac rhythm disturbances,
- Any other reported SAE, including death

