In keeping with the Bayesian nature of the trial design, we will use a Bayesian interim monitoring approach to determine whether systematic differences are emergent among the two treatment groups in the incidence of any of the adverse events listed above. Specifically, after every 40 babies enrolled in the trial have spent 24 hours post their final study transfusion, we will calculate the posterior probability that one group has higher incidence of any adverse events than another. In statistical terms, the treatment will be considered harmful (i.e., the DSMC may consider termination of the trial) if for a pre-specified threshold η , the posterior probability of treatment harm (in terms of the above adverse events) is greater than η ; in other words if the predictive probability $P(\theta > 1 | X) > \eta$, where θ denotes the relative risk favoring the treatment group and X is the data available. In order to allow for a liberal safety monitoring regime to ensure patient safety, we propose to take $\eta = 80\%$. However, we will also present the 95% credible interval for θ , as well as the entire posterior distribution for θ in a graphical fashion to the DSMC so that they have a full appreciation for the range of possible values of θ . All interim analyses will adjust for baseline level of encephalopathy, the stratification variable for this trial, whenever computationally feasible.

The choice of a prior distribution is essential and controversial in Bayesian analyses. Thus, we can compute the posterior probability of treatment harm and the posterior distribution of the associated relative risk under two sets of priors – (a) a non-informative prior that does not assume any substantive prior information about treatment differences in terms of the adverse events listed above, and (b) an informative prior based on treatment differences for these adverse events observed in the Phase I trial. However, we realize that the standard Bayesian approach of running the analysis with different priors provides only a partial solution, as the results on stopping are often inconclusive, especially when few data have accumulated. Instead of worrying about the selection of a single correct prior, we will also explore the use of a robust Bayesian approach which replaces a prior distribution with a class of priors and calculates the corresponding posterior probabilities for decision making²⁶.

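### The interim safety window closes by about 72 hours of age, so an infection or contaminated unit recognised later may be left out of the harm comparison

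*Combined protocol and SAP*

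**What the plan says.** Section 13.4 sets the scope of interim safety monitoring: the "primary focus of interim monitoring for this trial will be based on monitoring adverse events within 24 hours of cord blood infusion". It then lists the monitored events, Infectious Disease among them, "plus a composite (any of the listed events), on which statistical comparisons between the treatment groups will be based". Looks take place "after every 40 babies enrolled in the trial have spent 24 hours post their final study transfusion". The DSMC may consider stopping if the posterior probability of harm exceeds 80%, a threshold chosen "In order to allow for a liberal safety monitoring regime to ensure patient safety". One item carries a time limit of its own, "Pulmonary Hypertension, within the first 24 hours"; Infectious Disease has none.

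Section 8.1 releases product on a negative Gram stain and then covers a later result: "If sterility cultures, which will be performed on the collected cord blood at Duke University Stem Cell Laboratory (STCL), subsequently become positive", the clinical team is told and follow-up is planned. It allows that the infant may by then have stopped antibiotics. Section 8.3 covers shipped material: "Cryopreservation is dependent on receipt of cord blood or processed cord blood within 96 hours of collection at STCL at Duke University". It advises shipping as early as possible and lists sterility among the recorded unit characteristics.

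Adverse events are recorded from infusion onward (section 13.2), and the schedule in section 9 has a column headed "Rewarming through postnatal day 21". Infection is the first complication named in section 12.1. The definition of each event is left to MOP-01 Section 10.1, which is not part of the documents.

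**The concern.** A 24-hour window suits acute infusion reactions. It suits infection from a contaminated product less well, because the protocol itself expects the culture result to come later. No section says whether a positive unit culture, or an infection recognised after 24 hours, enters the harm comparison, or by which date it would be assigned.

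At stake is whether the DSMC's formal safety comparison covers a complication that the protocol names. Section 13.4 wants that comparison to be sensitive. Infection is likely to be a sparse item, so one or two events left outside the window can settle what its comparison shows.

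**Working it through.** The documents give no error rate or power for the harm rule, so there is no stated figure to reproduce. The check has four steps.

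**1. Timing.** Inputs: last dose by 48 h after delivery (section 8.4); window 24 h (section 13.4); receipt up to 96 h after collection (section 8.3); collection at about 0 h (section 8.1).

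Window close = final infusion + 24 h. Gap = receipt − window close.

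| Final infusion (h) | Window closes (h) | Gap if received at 48 h | at 72 h | at 96 h |
|---|---|---|---|---|
| 12 | 36 | 12 | 36 | 60 |
| 24 | 48 | 0 | 24 | 48 |
| 48 | 72 | −24 | 0 | 24 |

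The latest possible close is 48 + 24 = 72 h. Receipt at 96 h falls 96 − 72 = 24 h or more after any window has closed. Incubation comes on top, and its length is not stated. A negative gap means that the unit arrives inside the window, although a result by then is still not assured.

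**2. Would the data exist at a look?** Accrual is 60 to 80 infants per year (section 6). Forty infants take 40/80 × 12 = 6 months to 40/60 × 12 = 8 months. With an assumed culture lag of 5 to 14 days, infants without a result at a look number from 60 × 5/365 = 0.8 to 80 × 14/365 = 3.1. Nearly all results would be in hand. Any loss would come from the window being applied by date of recognition or result.

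**3. What capture does to the comparison.** Assumptions: equal arms of 20, no adjustment for encephalopathy level, and independent Beta(1,1) priors (section 13.4 does not specify its non-informative prior). With no control events, the control rate has posterior Beta(1,21), so P(harm) = 1 − E[(1 − p)^21], where p is the cell-arm rate.

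- 1 v 0: p ~ Beta(2,20), giving 1 − (20×21)/(41×42) = 0.756.
- 2 v 0: p ~ Beta(3,19), giving 1 − (19×20×21)/(40×41×42) = 0.884.

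Under Beta(0.5,0.5) the values are 0.822 and 0.930. One or two events decide whether 0.80 is passed.

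Now let a fraction c of an assumed 10-point excess be captured. For infection alone, the rates are 0.01 + 0.10c against 0.01. For the composite with base rate b, they are 1 − (1 − b)(1 − 0.10c) against b. The chance of passing 0.80 with 20 per arm is:

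| Comparison | c = 0 | c = 0.25 | c = 0.5 | c = 1 |
|---|---|---|---|---|
| Infection alone | 0.01 | 0.13 | 0.30 | 0.61 |
| Composite, b = 30% | 0.19 | 0.23 | 0.27 | 0.36 |
| Composite, b = 60% | 0.21 | 0.23 | 0.25 | 0.29 |
| Composite, b = 80% | 0.17 | 0.18 | 0.19 | 0.22 |

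The excess and the base rates are illustrations; the documents give neither.

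**4. Lag if infection is followed to day 21.** Infants under 21 days old at a look: 60 × 21/365 = 3.5 to 80 × 21/365 = 4.6.

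**The case against.** The best defence is that the text does not fix a strict window. Section 13.4 speaks of a primary focus. Pulmonary hypertension alone has its own 24-hour limit, which would be redundant if 24 hours bound every item. The catch-all for any other serious event has no limit in its own wording, and the 24 hours attached to the looks fix when a look happens. The definition in MOP-01 might let a clinical diagnosis, or the infant's own culture, count by onset date. Late positives are also handled outside the rule: the clinical team is notified, serious events are reported, and the DSMC has a general safety remit.

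Much of this stands, and it rules out three stronger readings that a reader might infer.

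- *Infection counts only within 24 hours.* The text does not say so. It gives no other window either, and the scope is set in section 13.4 and not in the manual.
- *Late recognition would be the usual case.* The 96 h limit governs cryopreservation of shipped units and is not a culture deadline. Prompt shipping is advised, units collected at the central site need no such transit, and no typical transit time is given. The documents support may, not usually.
- *The cell arm should show an excess.* The cell product is handled more, but placebo is made from the infant's own cord blood (section 8.2), so contamination at collection can reach both arms. No difference between arms is shown.

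The defence leaves one thing open: nothing tells the DSMC's statistician whether a later infection or positive culture belongs in the comparison.

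**Conclusion.** The point holds as a gap in the scope of the harm comparison. The window closes by about 72 h of age at the latest, and the unit's culture may not have reached the laboratory by then. Applied as written, the window can leave out later-recognised infection and contaminated units, although the data are recorded and would nearly all be available at looks 6 to 8 months apart.

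The timing follows from the documents. The effect on detection does not: it rests on the assumed 10-point excess, base rates, priors and capture fractions. Under those assumptions it is large for infection compared alone (0.61 to 0.30 when half the excess is captured) and modest for the composite (at most 0.36 against 0.19, full against no capture). How much is lost in practice depends on the MOP-01 definition and on the date used to assign an event, and the documents give neither.

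**What to change.** Leave the 24-hour composite and its 80% rule unchanged. Moving infection to a longer window inside the composite would mix two windows in one endpoint. Add to section 13.4, for each DSMC look:

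1. a separate comparison of Infectious Disease events from infusion through postnatal day 21, by arm and overall;
2. a table of positive central sterility cultures on infused units, by arm and overall;
3. a statement that both are assigned to the infant by infusion, not by result date, and that infants not yet at day 21 are carried to the next look.

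The overall column matters because contamination at collection could affect both arms and leave a between-arm comparison flat. The two displays complement each other: section 8.1 describes culture of the collected blood, so contamination introduced during processing might show only as infection in the infant.

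The cost is wording in section 13.4 and two tables in the DSMC report. Unit sterility and adverse events are already recorded. Day 21 is a convenient limit because the schedule already has it; it is not derived from any infection-specific figure. About 3.5 to 4.6 infants will have incomplete data for this item at each look, and some unrelated hospital-acquired infections will enter both arms.

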13.5. INTERIM MONITORING FOR EFFICACY OUTCOME

The relatively rare condition that this trial addresses means that it may take considerable time for this trial to enroll the requisite number of babies. Thus, even though the primary outcome is only available at 12 months corrected age, the enrollment period for the trial may make some interim efficacy data on the primary outcome available for monitoring by the DSMC. Note that because of the Bayesian nature of the trial design, interim efficacy looks at the data will not have any adverse Type I error consequences that are normally the case for a conventionally designed (or, ‘frequentist’) trial.

We propose to conduct one formal interim analysis of the accruing primary outcome data, examining both efficacy and futility, at a third of primary outcome accrual for this trial, provided that recruitment and intervention have not been completed by that point in time. The analysis for both efficacy and futility will adjust for baseline level of encephalopathy, the stratification variable for this trial, if computationally feasible

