A Phase II Multi-site Study of Autologous Cord Blood Cells for Hypoxic Ischemic Encephalopathy (HIE) IND 14753 (BABYBAC II)

Non-English language learners will be assessed by a bilingual examiner who has been certified or with the assistance of a qualified interpreter. Interpreters must be instructed to translate the Bayley instructions to the child verbatim and to not repeat instructions unless instructed to do so by the examiner. Language scores will not be derived for non-English language learners as the normative developmental progression of language milestones in other languages may not be accurately reflected on the Bayley Language Scales.

11.2.MRI

An MRI is routinely obtained on HIE infants between 7 – 28 postnatal days. Ideally the MRI will be done optimally at 10 days of life (but with an acceptable window between 7 days and 21 days of life as suggested by the 2014 revised guidelines for infants with HIE, to assess extent of injury) ²¹. Results from the standard of care MRI will recorded for the study.

11.3.NICU DISCHARGE

Tracking information will be recorded at discharge, and will include phone numbers and home address. All surviving infants will be followed for one year for the in-person assessment.

An attempt will be made at each site to obtain an autopsy in case of death both prior to and following NICU discharge. Autopsy results, if available, will be included in the case report forms.

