13.6. INTERIM ESTIMATION OF TREATMENT EFFICACY

This interim efficacy analysis will first evaluate whether the intervention is beneficial, equivalent, or harmful relative to usual care. A Bayesian logistic regression model will be fit to the data to obtain adjusted estimates of interim treatment efficacy, adjusting for the trial stratification variables.

A prior distribution is chosen in Bayesian analyses to provide an estimate of initial beliefs concerning the size of the potential treatment benefit. Thus, if one hopes that the results from the trial will influence the treatment of future patients, the prior distribution should represent the level of skepticism that is expressed by those clinicians that one seeks to influence. There are three principal types of prior we could use: (i) the uninformative, or reference prior, (ii) the skeptical prior and (iii) the enthusiastic prior. The uninformative prior represents a lack of clinical opinion as to the likely treatment difference, and in that sense contains no information about prior beliefs or other prior knowledge (eg. a relative risk for treatment benefit set at 1.0). A skeptical prior would be that overall effect of cord blood is actually harmful in this setting (i.e., a relative risk set higher than 1). An enthusiastic prior would be that the treatment is beneficial, as in the Phase I trial (relative risk set lower than 1).

It is generally useful to present the results of Bayesian analyses under several alternative prior distributions, so that the impact of differing levels of prior belief on the observed data may be reviewed. The uninformative prior has the advantage of corresponding roughly to the classical frequentist approach, and so this together with the skeptical and enthusiastic priors gives a broad and useful overview of the implications of terminating a clinical trial²⁷. Accordingly, we will use

A Phase II Multi-site Study of Autologous Cord Blood Cells for Hypoxic Ischemic Encephalopathy (HIE) IND 14753 (BABYBAC II)

all three prior distributions to present adjusted mean posterior relative risk (RR) estimates of treatment efficacy relative to survival free of cognitive impairment, along with corresponding 95% credible intervals for the same. These priors will be set at RR = 1.1 (skeptical prior), 1.0 (uninformative prior) and 0.625 (enthusiastic prior).

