13.7. INTERIM ESTIMATION OF TREATMENT FUTILITY

In addition to providing estimates of interim treatment efficacy, we will also conduct interim futility analyses for treatment efficacy. For this purpose, at each interim safety look, we will use the available data to calculate the posterior probability of concluding that the probability of survival free of cognitive impairment in the cord blood group would be higher than in the placebo group (i.e., the mean posterior RR for treatment benefit is greater than 1.0), if the trial continued until 120 patients were randomized and had their primary outcomes evaluated. In order to provide a more conservative basis for this estimate, and also to convince even those who strongly believed in this intervention at the outset, we will primarily use an optimistic prior for this calculation, with the prior belief set at a level of treatment benefit observed in the Phase I trial. However, in order to provide a broad overview and to explore the robustness of this estimate with respect to prior assumptions, this probability will also be calculated and presented for the two other prior distributions (skeptical and uninformative).

The DSMC may consider proposing termination of the trial for futility if this posterior probability of observing any treatment benefit, if the trial continued to full primary outcome accrual, is less than 10%.

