15.2. ESTIMATES OF AVAILABLE AND REQUIRED SAMPLE SIZE

In our phase I study to date, 16 of 25 (64%) cell recipients with known one year outcomes have survived with all three Bayley III assessments (Cognitive, Motor, and Language) ≥ 85 , and 25 of 63 (40%) of the cooled-only infants with known one year outcomes has survived with all three Bayley III domain scores ≥ 85 . (13) We acknowledge the limitations of a one year Bayley score, but would note that our rate of survival with Bayley scores ≥ 85 among cooled-only infants is consistent with the previously reported Whole Body Hypothermia studies rates of survival at 12–24 months without moderate or severe impairment (1 -4).

For the phase II study, rather basing the sample size on effect size, we would propose a Bayesian approach as used in the NRN Late Hypothermia study. Because this is phase II where our aim is to detect a trend favoring cell recipients, and to accumulate data that will inform design and sample size calculations for a phase III study of efficacy, we anticipate that two years of enrollment would provide approximately 120-160 infants, 60-80 in each group.

Control	Cell Recipients	95% Confidence Interval	Power
0.6	0.30	0.45	0.92
0.6	0.35	0.48	0.81
0.6	0.40	0.51	0.62
0.6	0.45	0.54	0.38
0.6	0.60	0.54	0.056

The Bayesian analysis will permit calculation of a probability of treatment benefit. Within the range of an active group proportion of 0.3 to 0.45, the average 95% credible interval width ranges from 0.45 to 0.54 when the control group has a proportion having the primary outcome (death or Bayley III scores < 85) of 0.6. If the decision rule for declaring a win is the posterior 95% credible interval must exclude 1, then the design has power ranging from 0.92 to 0.38 with a Type 1 error of about 0.056.

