15.3. STATISTICAL ANALYSIS PLAN

All statistical analyses, including interim monitoring, will be conducted using the intent to treat principle, unless explicitly specified otherwise for certain secondary and/or post-hoc analyses. A Bayesian approach will be used for conducting the primary analysis in this trial. We propose to apply a log-binomial regression model and a neutral prior that will be centered at RR=1.0 to final

A Phase II Multi-site Study of Autologous Cord Blood Cells for Hypoxic Ischemic Encephalopathy (HIE) IND 14753 (BABYBAC II)

efficacy and safety data, where final data is defined as data contained in the study database after database lock. Database lock will occur either after 160 infants have completed the study or the study is terminated early for efficacy, futility, or safety. In addition to using a neutral prior, final analyses on locked data and some interim analyses will develop posterior distributions using skeptical (centered at $RR = 1.1$) priors and/or enthusiastic (centered at $RR = 0.625$) priors as well. In all analyses, MCMC methods will be used to sample from the Posterior distribution.

All analyses will involve estimating a Posterior distribution based on a log-binomial regression model with covariates and MCMC methods. In addition to estimating the treatment effect on the log relative risk scale, the log-binomial regression will adjust for level of encephalopathy. For the intercept and the encephalopathy terms, Normal (mean = 0, sd=100) priors will be used. For the term representing the log relative risk, skeptical, neutral, and enthusiastic priors will be used to estimate posterior distributions for the relative risk.

With respect to the primary efficacy endpoint, the estimated Posterior distribution of relative risk based on the data and the neutral prior will be used to determine posterior probabilities of >0 , >10 and $>20\%$ decrease in death or moderate/severe disability, as well as graphical displays of the Posterior distribution and appropriate 95% credible intervals for the relative risk. In addition to adjusting for level of encephalopathy and center in the log-binomial model, the final analysis of efficacy will also perform sensitivity analyses concerning possible treatment effect confounders present at randomization. All additional covariates added to the model will utilize Normal (mean=0, sd=100) priors.

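### The Bayesian label does not exempt the one-third efficacy look from Type I error consequences (the effect is small), and the Section 15.2 table fits about 120 infants rather than 160, with one inconsistent width

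*Combined protocol and SAP*

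**What the plan says.** - **Section 13.5** plans one formal look at a third of primary outcomes, for efficacy and futility, to be held only if recruitment and intervention are not yet complete. It contrasts the design with a frequentist one and makes this claim: "because of the Bayesian nature of the trial design, interim efficacy looks at the data will not have any adverse Type I error consequences".
- **Section 13.6** lets the DSMC consider proposing a stop for benefit if the upper 95% credible limit for the relative risk (RR), under the skeptical prior, is below 1. Sections 13.6 and 15.3 give the centres of the three treatment priors (1.1, 1.0 and 0.625) but not their SDs. The SD of 100 in Section 15.3 applies to the intercept and covariate terms only.
- **Section 15.2** expects that "two years of enrollment would provide approximately 120-160 infants, 60-80 in each group". Its table names no sample size. The text below the table puts the rule conditionally, "If the decision rule for declaring a win is the posterior 95% credible interval must exclude 1", and gives these operating characteristics for it: "then the design has power ranging from 0.92 to 0.38 with a Type 1 error of about 0.056".
- **Section 15.3**: "Database lock will occur either after 160 infants have completed the study or the study is terminated early for efficacy, futility, or safety".
- **Section 11.3**: "All surviving infants will be followed for one year for the in-person assessment".
- **Section 13.7** projects futility as "if the trial continued until 120 patients were randomized and had their primary outcomes evaluated".

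**The concern.** Type I error belongs to a decision rule under repeated sampling, whatever inferential framework produced the rule. Section 15.2 accepts this by quoting one. An extra opportunity to stop for benefit can add false benefit conclusions. Whether it does depends on how tight the skeptical prior is, whether the look takes place, and what follows a stop. The word Bayesian settles none of these.

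The Section 15.2 table raises a second question. A reader cannot tell which sample size, prior or number of looks its figures describe. Section 15.2 says the trial is meant to inform the design and sample size of a Phase III study, so its own operating characteristics should be traceable.

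**Working it through.** **Inputs.** Section 15.2: outcome proportion (death or a Bayley score below 85) 0.6 in controls; 0.30, 0.35, 0.40, 0.45 or 0.60 (null) on cells; win if the 95% interval for RR excludes 1. Sections 13.5 and 13.6: look at one third (27 of 80 per arm), stop if the upper limit is below 1 under a prior centred at RR 1.1. Section 6: 60 to 80 infants a year. Section 8.5.6: outcome at 12 to 16 months. *Assumed, because not stated:* skeptical SD on log RR from 0.2 to vague; flat final prior; even accrual. Covariate adjustment is left out, as is futility stopping, which can only lower false benefit.

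**Step 1: reproduce the table.** On the log scale SE² = (1−p₁)/(n·p₁) + (1−p₀)/(n·p₀), and width = RR·(e^{1.96·SE} − e^{−1.96·SE}). For n = 60, p₁ = 0.30: SE² = 0.7/18 + 0.4/36 = 0.050, SE = 0.2236, width = 0.5 × (1.550 − 0.645) = 0.452, against 0.45 stated. Exact binomial enumeration, one analysis, flat prior, gives power / mean width:

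| Cells | Stated | 60 per arm | 80 per arm |
|---|---|---|---|
| 0.30 | 0.92 / 0.45 | 0.924 / 0.458 | 0.971 / 0.392 |
| 0.35 | 0.81 / 0.48 | 0.803 / 0.489 | 0.889 / 0.419 |
| 0.40 | 0.62 / 0.51 | 0.612 / 0.517 | 0.715 / 0.443 |
| 0.45 | 0.38 / 0.54 | 0.393 / 0.542 | 0.470 / 0.465 |
| 0.60 (null) | 0.056 / 0.54 | 0.050 / 0.606 | 0.046 / 0.520 |

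Over the first four rows the largest gaps from the stated figures are 0.013 (power) and 0.009 (width) at 60 per arm, against 0.095 and 0.075 at 80 per arm.

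**Step 2: the null row.** By the formula at n = 60, the 0.45 row has SE² = 0.55/27 + 0.4/36 = 0.0315 and width 0.532. The null row has SE² = 2 × 0.4/36 = 0.0222 and width 0.593: the SE is smaller, but RR is 1 rather than 0.75. The exact averages are 0.542 and 0.606. The null row is 7 to 12% wider than the 0.45 row at every size checked from 40 to 100 per arm and every neutral SD tried (0.35, 0.5, 1, flat). With a flat prior, a null width of 0.54 belongs to 74–75 per arm, where the 0.45 row would be 0.48.

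**Step 3: is the look held?** Time of look = (N/3)/rate × 12 + 12 or 16 months. Recruitment ends at N/rate × 12.

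| N | Rate per year | Look (outcome at 12 / 16 mo) | Recruitment ends |
|---|---|---|---|
| 120 | 60 | month 20 / 24 | month 24 |
| 120 | 80 | month 18 / 22 | month 18 |
| 160 | 60 | month 22.7 / 26.7 | month 32 |
| 160 | 80 | month 20 / 24 | month 24 |

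Recruitment is complete at the look in three of four cases at 120 and one of four at 160. Two of the three, and the one, are exact ties. Slower accrual makes the look more likely.

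**Step 4: effect of the look, 80 per arm, 0.6 in both arms.** At 27 per arm s² = 2 × 0.4/(27 × 0.6) = 0.0494, so s = 0.222. With skeptical SD τ, stopping needs a benefit z-value of about s·[1.96·√(1/s² + 1/τ²) + ln(1.1)/τ²]. For τ = 0.35 this is 0.222 × (10.45 + 0.78) = 2.49. Exact one-sided false benefit without the look is 0.0228. With it:

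| τ | z needed | Stop counts as benefit | Final rule on the 57 per arm enrolled at the stop |
|---|---|---|---|
| 0.2 | 3.46 | 0.023 | 0.0228 |
| 0.35 | 2.49 | 0.0246 | 0.0232 |
| 0.5 | 2.23 | 0.0283 | 0.0238 |
| 1 | 2.03 | 0.036 | 0.0244 |
| vague | 1.96 | 0.0384 | 0.0246 |

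The 57 per arm is the smallest enrolment in Step 3 at N = 160: 22.67/12 × 60 = 113 infants. At 67 per arm the last column is at most 0.024. The added risk in the third column is 0.0246 − 0.0228 = 0.0018 at τ = 0.35, 0.0055 at 0.5, and 0.0156 if vague. In the last column it is at most 0.0018. With the logistic model of Section 13.6, the third column is 0.023 at τ = 0.5 and 0.029 at τ = 1.

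**The case against.** **The sentence can be read charitably.** A posterior distribution does not depend on the stopping rule. That is true, but the sentence speaks of Type I error, which can depend on it.

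**No win is formally declared.** Section 15.2 states its rule conditionally, Section 15.3 reports posterior probabilities without a threshold, and the stop is advisory. Locked data then go to a neutral-prior analysis, and Section 11.3 follows all survivors. This largely stands. The plan nowhere equates a stop with a benefit conclusion, although it also does not say whether lock waits for infants still in follow-up.

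**A vague skeptical prior is not skeptical.** Section 13.6 chooses this prior to be conservative, so the upper figures in Step 4 are an outer bound, not the expected case. This stands.

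**The sample size is given next to the table.** Only as a range of 60 to 80 per group. A neutral prior with SD 0.35 at 80 per arm would bring the powers close (0.944/0.828/0.632/0.394), but not the widths (0.403 to 0.444) or the null error (0.032).

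**Stronger readings.** A reader might infer that the look materially inflates false positives, that the trial is underpowered, or that the quoted 0.056 leaves the look out. The documents support none of these. The inflation is small in every plausible case. The table mismatch runs in the trial's favour at 160. And 0.056 cannot show whether the look was simulated: the number of simulations is not given, and at 60 per arm the two-sided rate runs from 0.050 without the look to 0.065 at its most extreme.

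**Conclusion.** The Section 13.5 sentence claims a property that being Bayesian does not confer. Any protection comes from the spread of the skeptical prior, the proviso on the look, and follow-up after a stop.

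One-sided, the added false-benefit risk at 80 per arm is:
- zero if the look is skipped;
- at most about 0.002 if enrolled infants are followed and the final rule decides;
- about 0.002 to 0.005 if a stop counts as benefit, with skeptical SD 0.35 to 0.5 on the log-RR scale;
- roughly 0.015 only with a near-vague skeptical prior.

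These rest on assumed SDs and a normal approximation for log RR.

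The Section 15.2 powers and first four widths describe about 120 infants and are conservative for 160. The null-row width is inconsistent with them. It looks like a repeat of the row above, which is an inference, and neither the stated power range nor the width range quoted in the text depends on it. This is a correction of stated figures and of one claim; it does not call the design into question.

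**What to change.** 1. In Section 13.5, replace the sentence with a simulated Type I error that includes the look, its recruitment proviso and the skeptical prior SD used. The simulation must also state what it assumes after a benefit stop: whether the stop is itself a conclusion, or the final rule is applied once enrolled infants have outcomes.
2. In Section 15.2, restate the table by sample size (120 and 160) and prior, and correct the null-row width.
3. Reconcile the 120 patients in Section 13.7 with the 160 in Section 15.3.

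The cost is a short simulation and a few lines of text, with no change to conduct. The stated Type I error may become slightly less favourable; stated power and precision at 160 become more favourable.
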